## 10.2 Key Secondary Efficacy Endpoint(s) and Analysis

The key secondary endpoint is defined as the proportion of subjects with all-cause graft failure at 4 years following treatment of the initial qualifying AMR episode. The graft failure is defined as 1 or more of the following: (1) institution of permanent dialysis, (2) current transplant nephrectomy, or (3) clinical determination of cessation of kidney graft function in any subject that had received a pre-emptive kidney transplant prior to starting dialysis. The FAS will be used for analyzing the key secondary endpoint. Subjects who discontinued prior to 4 years (i.e. Month 48) will be considered 'missing assessment for graft failure at 4 years' and assigned as failures.

The hypothesis of the key secondary endpoint will only be tested if the testing for the primary endpoint of new or worsening TG at 6 months is statistically significant.

The key secondary analysis specified below will be performed based on the FAS. As a sensitivity analysis, the key secondary analysis will be also performed based on Per-protocol Analysis Set-2.

The key secondary endpoint will be presented as the proportion of subjects with all-cause graft failure, and their difference between treatments ( $\Delta_{Cinryze-Placebo}$ ) is defined as follows:

$$\Delta_{Cinryze-Placebo} = \Pi_{Cinryze} - \Pi_{Placebo}$$

Where  $\Pi_{Cinryze}$  is the proportion of all-cause graft failure post-treatment in the CINRYZE group and  $\Pi_{Placebo}$  is the proportion of all-cause graft failure post-treatment in the placebo group.

The analysis will employ a type I error rate of 0.025 to test null hypothesis:

$$H_0 : \Pi_{Cinryze} - \Pi_{Placebo} \geq 0$$

Against the 1-sided alternative:

$$H_a : \Pi_{Cinryze} - \Pi_{Placebo} < 0$$

The key secondary endpoint will have 3 analyses (2 interim and 1 final), at approximately 50% (~26 events), 75% (~39 events) and 100% (~51 events) of the targeted all-cause graft failure. The purpose of the interim analyses is to consider early stopping of the study for claiming of efficacy.

The difference between treatments will be evaluated by a Fisher's Exact test. If the p-value from the test is  $\leq 0.0030$  at first interim analysis (~50% of events), or  $\leq 0.0075$  at the second interim analysis (~75% of events), or  $\leq 0.0221$  at the final analysis (~100% of events), it will be concluded that CINRYZE is efficacious based on the proportion of subjects with all-cause graft failure and the result will serve as confirmatory evidence of clinical benefit based on all enrolled subjects.

Sensitivity analyses will be done at final analysis by using multiple imputation (MI) assuming missing at random (MAR) to assign missing key secondary endpoint and/or by using Cochran–Mantel–Haenszel (CMH) test for treatment effect. The CMH model will assess the treatment effect with controlling for (1) donor characteristic (living vs deceased), (2) baseline AMR severity (severe vs mild to moderate), and possibility (3) time to onset of qualifying AMR from current transplant ( $>100$  days vs  $\leq 100$  days) if degree of freedom allows. All the sensitivity analyses defined below will be based on the FAS.

	Statistical Test	Logic to assign the missing assessments for graft failure at 4 years (i.e. discontinued prior to 4 years)
Key Secondary Analysis Model	Fisher's Exact	Assign failure for subjects who discontinued prior to 4 years.
Sensitivity analysis 1	Fisher's Exact	MI for subjects who discontinued prior to 4 years.
Sensitivity analysis 2	CMH	Assign failure for subjects who discontinued prior to 4 years.
Sensitivity analysis 3	CMH	MI for subjects who discontinued prior to 4 years.

For multiple imputation for the key secondary endpoint, a monotone missing pattern will be assumed. The prediction model will consider treatment group, , AMR severity baseline, donor characteristic as factors with available post-dose eGFR results incorporated. The imputation seed will be 83789524 and number of imputations will be set as 100.

For sensitivity analysis 1, multiple imputation will be used to impute the key secondary endpoint outcome for all subjects who discontinued prior to 4 years. The p-values from Fisher's Exact tests will be computed for each imputed dataset and transformed to  $\chi^2$ -distribution with  $df = 2$  using Fisher's transformation as:

$$\Psi^{(m)} = -2 \log(p^{(m)}) \sim \chi_2^2$$

where  $p^{(m)}$  is the p-value from Fisher's Exact test and  $\Psi^{(m)}$  is the transformed  $\chi^2$ -distribution for the  $m$ -th ( $m = 1, 2, \dots, 100$ ) imputed dataset.

Wilson-Helferty transformation (Wilson & Helferty, 1931; Goria, 1992) will be used to transform the  $\chi^2$ -distribution to an asymptotic normal distribution with mean 0 and variance 1, as following:

$$Z_{WH}^{(m)} = \frac{\left( \frac{\Psi^{(m)}}{df} \right)^{1/3} - \left( 1 - \frac{2}{9 \times df} \right)}{\left( \frac{2}{9 \times df} \right)^{1/2}} \quad (\text{Formulae 5})$$

where  $\Psi^{(m)}$  is the  $\chi^2$ -distributed statistic from the  $m$ -th imputed dataset,  $df$  is the number of degrees of freedom associated with  $\Psi^{(m)}$ , and  $Z_{WH}^{(m)}$  is the transformed value.

Then, the transformed normal statistic  $Z_{WH}^{(m)}$  for each imputed dataset will be combined using multiple imputation analysis to yield the combined test statistic  $Z_{WH}$ .

For sensitivity analysis 2, subjects who discontinued prior to 4 years will be assigned as graft failure. The CMH test will be performed to assess the treatment effect with controlling for baseline AMR severity and donor characteristic.

For sensitivity analysis 3, multiple imputation will be used to impute the key secondary endpoint outcome for all subjects who discontinued prior to 4 years. The CMH test will be performed to assess the treatment effect controlling for baseline AMR severity and donor characteristic. The CMH general association statistics will be computed for each imputed

dataset and transformed to asymptotic normal as shown in formulae 5. Then, the transformed normal statistic  $Z_{WH}^{(m)}$  for each imputed dataset will be combined using multiple imputation analysis to yield the combined test statistic  $Z_{WH}$ .

Descriptive statistics for the key secondary efficacy outcome will be provided for the following subgroups: donor status at transplant, AMR severity at baseline, age, sex, and race.

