The purpose of the second interim analysis is to allow early stopping if the primary endpoint is not met or for claiming of efficacy based on new or worsening TG within at 6 months of initiation of treatment. This analysis will be done when a required number of subjects (based on the first interim analysis) complete the Month 6 TG assessments. If the result of the second interim analysis is statistically significant at 0.0249, the primary null hypothesis will be rejected. The test statistic at the second interim stage will be derived using CHW method and specified in the interim SAP.

The efficacy boundary of TG at 6 months of initiation of treatment will be pre-specified by Haybittle-Peto boundary (Haybittle 1971; Peto et al. 1976). The alpha level of 0.0001 is to be spent at the first interim analysis in developing the efficacy boundary of the second interim analysis of TG at 6 months of initiation of treatment. The overall significance level for the efficacy analysis of TG at 6 months of initiation of treatment will be preserved at 0.025 (1-sided test) by using a significance level of 0.0249 for the second interim analysis.

If the result of the second interim analysis of the primary endpoint indicates significant treatment effect on TG at 6 months of initiation of treatment, the study will continue to assess the long-term study outcomes including the key secondary endpoint (ie, proportion of subjects with all-cause graft failure).

For the key secondary endpoint, the study information is event based. The study will continue until approximately 51 confirmed clinical events are reached unless stopped prematurely based on findings at an interim analysis or the last enrolled subject has been followed for 4 years. There will be 3 analyses (2 interim and 1 final) of proportions of subjects with all-cause graft failure, at approximately 50% (~26 events), 75% (~39 events), and 100% (~51 events) of the study information. The purpose of the 2 interim analyses is to allow early stopping of the study for overwhelming efficacy and assessing safety of the treatment. An alpha spending function approximating the O'Brien-Fleming boundary shape (O'Brien and Fleming 1979) will be employed to maintain an overall significance level at 0.025. The test statistics and boundary values for decision making at the 3 analyses (2 interim and 1 final) will be specified in the SAP.

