9.8.2 Secondary Efficacy Endpoints

9.8.2.1 Key Secondary Efficacy Endpoint

The key secondary endpoint is defined as the proportion of subjects with all-cause graft failure (ie, return to permanent dialysis and/or removal of the transplanted kidney and/or clinical determination of cessation of graft function) at 4 years following treatment of the initial qualifying AMR episode. The FAS population will be used to report the efficacy data for all-cause graft failure. Subjects who do not have the key secondary efficacy endpoint assessed post-dose will be assigned as failures.

The proportion of subjects with all-cause graft failure will be summarized by treatment group. Subjects with an assessment of all-cause graft failure or who drop out due to graft failure will be included in the hypothesis testing.

The test statistics and boundary values for decision making at the 3 analyses (2 interim and 1 final) will be specified in the SAP.

The null hypothesis for the proportion of subjects with all-cause graft failure post-treatment will be tested at the overall accumulative alpha level of 0.025 (1-sided test). This hypothesis will only be tested if testing for the primary endpoint of new or worsening TG at 6 months of initiation of treatment is statistically significant.

A number of sensitivity analyses will be performed to assess any impact on the key secondary endpoint results, inference, and conclusions due to missing data. In addition, descriptive analyses on the key secondary endpoint will be provided in selected subgroups.

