study data. Following the Month 6 evaluation, subjects will enter a long-term follow-up stage of the protocol, which will include allograft function evaluations every 6 months up to a maximum of 4 years. The duration of the study will be event driven, and is based upon an assumption that there will be approximately 51 all-cause graft failures. The study will continue until 51 such events are accrued and adjudicated by the nephrology EAC. However the maximum amount of time each subject will be followed in the study will be 4 years post initial treatment with investigational product.

Resolution will be achieved when, after treatment, the local eGFRMDRD value increases to at least within 20% or above the eGFRMDRD value collected as a pre-AMR baseline. If an AMR episode is diagnosed, in absence of significant decline ( $\geq 20\%$ ) of eGFR from pre-AMR baseline, a follow-up biopsy within 3 months is recommended in order to assess resolution.

Recurrence is defined as biopsy-proven new evidence of AMR upon resolution of the previous AMR episode. Investigators will also be asked to record the date of recurrence of AMR, when applicable. During the first 6 months of the study only, if the qualifying AMR episode resolves and there is new biopsy-proven acute AMR per protocol definition in the inclusion criteria, the subject may be retreated at the investigative site with the same investigational product to which they were originally randomized as well as DSA reduction treatment and sucrose-free IVIg per protocol. Between the qualifying biopsy that is diagnostic for a recurrent episode of AMR and the first retreatment dose of investigational product, subjects will complete a subset of the screening procedures and follow the assessments noted in the schedule of assessments (Screening through Day 25) for each new episode of AMR occurring during the first 6 months of the study. Retreatment should occur as soon as possible within 7 days of the biopsy that defined the new AMR episode. Retreatment may not occur after the first 6 months of the study. Biopsies at Month 6 following retreatment will not be necessary. The only mandated follow-up biopsy will be at Month 6 after initial treatment.

The effect on the quality of life will be measured by using the EuroQoL Group 5-Dimension 5-Level Self-report Questionnaire (EQ-5D-5L).

[figure not shown]

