**Table 2 Schedule of Assessments (Month 3 through Month 48 [End of Study])a**

Study Procedure	Post-Treatment Evaluations									EOS/Month 48 or at patient discontinuation if after Month 6 (±28 days) b
	Month 3 (±21 days) b	Month 6 (±21 days) b	Month 12 (±21 days) b	Month 18 (±28 days) b	Month 24 (±28 days) b	Month 30 (±28 days) b	Month 36 (±28 days) b	Month 42 (±28 days) b	Early Discontinuation Visit Between Day 13 & Month 6	
Presence/absence of diabetes		✓								✓
Body Weight	✓	✓	✓	✓	✓	✓	✓	✓	✓	✓
BUN & Serum Cr with eGFR (both central and local lab) c	✓	✓	✓	✓	✓	✓	✓	✓	✓	✓
Central lab Proteinuria: Spot urine protein, urine Cr and urine protein/urine creatinine ratio	✓	✓	✓	✓	✓	✓	✓	✓	✓	✓
Kidney allograft biopsy & submission of pathology slides & images d		✓							✓	
Central lab Immunogenicity (anti-C1 INH antibodies)	✓	✓	✓ e		✓ e					
Central lab DSA identification f	✓	✓	✓	✓	✓	✓	✓	✓	✓	✓
Concomitant medications g	✓	✓	✓	✓	✓	✓	✓	✓	✓	✓
Adverse event monitoring h	✓	✓	✓	✓	✓	✓	✓	✓	✓	✓
Renal allograft assessment	✓	✓	✓	✓	✓	✓	✓	✓	✓	✓
Subject survival status	✓	✓	✓	✓	✓	✓	✓	✓	✓	✓
EQ-5D-5L	✓	✓	✓	✓	✓	✓	✓	✓		✓
Health Resource Utilization	✓	✓	✓	✓	✓	✓	✓	✓		✓

BUN=blood urea nitrogen; C1 INH=C1 inhibitor; Cr=creatinine; DSA=donor-specific antibody; eGFRMDRD=estimated glomerular filtration rate calculated by the Modification of Diet in Renal Disease; EOS=End of Study Visit; EQ-5D-5L= EuroQoL Group 5-Dimension 5-Level Self-report Questionnaire; SAE=serious adverse event; TG=transplant glomerulopathy

a The duration of the study will be event driven, and is based upon an assumption that there will be approximately 51 all-cause graft failures including death. The trial will continue until 51 such events are accrued and adjudicated by the independent, blinded nephrology EAC. See Section 9.5.1 of the protocol for additional details. However the maximum amount of time each subject will be followed in the study will be 4 years post initial treatment with investigational product. Subjects will complete visits every 6 months until the study is ended. If the study is stopped prior to the last enrolled subject completing Month 48, all subjects who have not reached Month 48 will be asked to return to the investigational site for their End of Study (EOS) visit.

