## 2.6 Multiplicity Adjustments for Type I Error Control

To control the overall Type I error, the primary and key secondary endpoint will be tested hierarchically with a fixed sequence approach. The study will continue to assess the key secondary endpoint only if the primary null hypothesis has been rejected. Thus, the significance of the key secondary endpoint is contingent, and no adjustment for multiple endpoints is needed.

The primary endpoint will have 2 analyses (1 interim and 1 final for the primary endpoint). The first interim analysis is for futility and sample size recalculation. The second interim analysis, which serves as the final analysis for the primary endpoint, is for the assessment of efficacy (new or worsening TG at 6 months). The alpha level of 0.0001 is to be spent at the first interim

analysis in developing the efficacy boundary of the second interim analysis of TG at 6 months. The overall significance level for the efficacy analysis of primary endpoint will be preserved at 0.025 (1-sided test) by using a significance level of 0.0249 for the second interim analyses. The difference between treatments will be evaluated by using the CHW weighted test statistic (Cui et al., 1999).

The key secondary endpoint will have 3 analyses (2 interim and 1 final), at approximately 50% (~26 events), 75% (~39 events) and 100% (~51 events) of the targeted all-cause graft failure. The Hwang-Shih-DeCani alpha spending function with phi = -4, which is similar to the boundaries from the O'Brien-Fleming method, will be used for the unequal spaced timing of analysis. Using this approach requires  $z \geq 2.75$  (or equivalently  $p \leq 0.0030$ ) to consider stopping the study for a positive treatment effect at the first interim analysis (~50% of events),  $z \geq 2.43$  (or equivalently  $p \leq 0.0075$ ) to consider stopping the study for a positive treatment effect at the second interim analysis (~75% of events), and  $z \geq 2.01$  (or equivalently  $p \leq 0.0221$ ) to claim efficacy at the final analysis (~100% of events), as shown in the table below. This approach maintains a fixed sample p-value close to 0.025 (1-sided test) at the final analysis and an overall significance level at 0.025.

Analysis	Proportion of Targeted Number of Events	Z Scale	p-value (1-sided)
Interim 3	50%	2.751	0.0030
Interim 4	75%	2.428	0.0075
Final	100%	2.012	0.0221

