### **4.6 Per-protocol Analysis Set-2 (PPS2)**

The Per-protocol Analysis Set-2 will consist of all subjects in the FAS who have taken at least 5 of the 7 planned doses, are assessed for graft failure at 4 years, or have shown graft failure within 4 years, or died, and do not have predefined major protocol deviations that may affect the key secondary endpoint.

These protocol deviations will be identified prior to unblinding of the study.

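### The key secondary endpoint is a proportion at 4 years, but the event-driven looks and closure usually come before all subjects reach Month 48; the crude Fisher test ignores follow-up time and Per-protocol Set-2 selects on outcome

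*SAP*

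**What the plan says.** The objective (Protocol 2.2.2, SAP 3.2) and the endpoint are tied to a fixed time: "The key secondary endpoint is defined as the proportion of subjects with all-cause graft failure at 4 years" (SAP 10.2).

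The calendar is tied to events. Protocol 9.5.1: "For the key secondary endpoint, the study information is event based". SAP 2.1: "The study will continue until 51 such events are accrued and adjudicated by the nephrology EAC". Follow-up is capped at 4 years per subject, and the study ends without 51 events only on an interim finding or once the last subject has 4 years (SAP 2.5). Table 2, footnote a, foresees closing before some subjects get there: "all subjects who have not reached Month 48 will be asked to return to the investigational site" for an end-of-study visit.

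The looks are at about 26, 39 and 51 failures. SAP 2.6 sets the boundaries with the "Hwang-Shih-DeCani alpha spending function with phi = -4, which is similar to the boundaries from the O'Brien-Fleming method", giving one-sided p of 0.0030, 0.0075 and 0.0221. At each look, "The difference between treatments will be evaluated by a Fisher's Exact test" (SAP 10.2).

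SAP 10.2 counts subjects who discontinued before 4 years as failures. It gives no rule for a subject with a working graft who is still on study at a look, or who is sent home by the closure itself. Censoring is defined only in SAP 10.3, for the separate time-to-event endpoints.

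Per-protocol Set-2 (SAP 4.6, Protocol 9.7) requires at least 5 of 7 doses, no major deviation, and that subjects "are assessed for graft failure at 4 years, or have shown graft failure within 4 years, or died".

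**The concern.** A proportion at 4 years needs every subject's status at 4 years, whereas an event-driven trial stops when enough failures have occurred, whatever the follow-up. A crude 2x2 table at that moment mixes subjects with 4 years of follow-up and subjects with much less, so the rates depend on how fast subjects were enrolled. Fisher's test also discards the timing of the failures.

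Set-2 has a further problem. Among subjects who meet the dose and deviation conditions, a failure or death enters at any time, but a working graft enters only once it has been assessed at 4 years. Closing at event 51 therefore removes working grafts and keeps failures. SAP 10.2 names this set as a sensitivity analysis for the endpoint.

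Protocol 9.8.1 requires significance on this endpoint for a successful study, so its reported rates would carry the claim of clinical benefit.

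**Working it through.** **Inputs.** From SAP 2.5: AMR-related failure 64% v 25%, other-cause failure 12% in each arm, 100 evaluable subjects for 90% power, 10% drop-out, 112 randomised 1:1, 51 events. From SAP 2.6: the three nominal p-values. Assumed, because the documents give no figure: constant hazards and uniform accrual. Protocol Synopsis says only that enrolment was planned for 2015 through 2017 and will be extended, so lengths of 3 to 8 years were used.

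**1. The plan's own figures reproduce.**
- All-cause failure: 1 - 0.36 x 0.88 = 68.3%; 1 - 0.75 x 0.88 = 34.0%.
- Sample size for 68% v 34%, one-sided 0.025, 90% power, with continuity correction: 50 per arm, so 100. Allowing for drop-out: 100/0.90 = 111.1, so 112.
- Events: 50 x 0.68 + 50 x 0.34 = 34 + 17 = 51.
- Hwang-Shih-DeCani (-4) at 50/75/100%: p = 0.0030, 0.0075, 0.0221.

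**2. Why closure tends to come early.** The 51 is the 4-year count in 100 fully followed subjects, but 112 are randomised.
- Without drop-out, 56 x 0.68 + 56 x 0.34 = 57.1 failures are expected by 4 years.
- With drop-out, yearly hazards are -ln(0.32)/4 = 0.2849 (placebo), -ln(0.66)/4 = 0.1039 (CINRYZE) and -ln(0.90)/4 = 0.0263 (drop-out).
- Failure seen before drop-out, placebo: 0.2849/0.3112 x (1 - 0.32 x 0.90) = 65.2%.
- Failure seen before drop-out, CINRYZE: 0.1039/0.1302 x (1 - 0.66 x 0.90) = 32.4%.
- Expected count: 56 x (0.652 + 0.324) = 54.7, still above 51.

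**3. Status at closure.** Simulation with 112 subjects, 10% drop-out and 3 to 8 years' accrual:

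| Quantity | Result |
|---|---|
| Event 51 closes the study early | about 77-80% of runs |
| Working grafts cut off short of Month 48, average over all runs | about 27 (3 years) to 18 (8 years) |
| Adjudicated failures, true 68% v 34% | about 61% v 29% |
| Set-2 | about 80% v 53% (3 years) to 75% v 42% (8 years) |
| Power over three looks, Fisher, drop-outs as failures | about 84-86% |
| Power over three looks, log-rank, drop-outs censored | about 92-94% |
| Fisher rejection when the arms are equal | about 1.5% |

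By step 2, part of the shortfall in the third row is drop-out (68 to 65, 34 to 32); the rest (65 to 61, 32 to 29) is early closure. Counting drop-outs as failures and closed-out grafts as non-failures gives about 66% v 37% (accrual 2 to 5 years): 29 points instead of 34, and still not a 4-year rate.

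**4. The interim looks.** With accrual over 2 to 5 years, 0-3% of subjects have reached 4 years at 26 events and 1-25% at 39.

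**5. What a time-to-event analysis gives.**
- Hazard ratio: ln(0.66)/ln(0.32) = 0.365.
- Schoenfeld power with 51 events: Phi(|ln 0.365| x sqrt(51)/2 - z) = Phi(3.60 - 1.96) = 95.0% at 0.025, and Phi(3.60 - 2.01) = 94.4% at 0.0221.
- Events needed for 90% power: 42 (Schoenfeld) or 49 (Freedman), so 51 is enough.
- On simulated data (accrual 2 to 5 years), Kaplan-Meier at 4 years gives 69% v 35% against the true 68% v 34%.

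**The case against.** Several points on the other side stand.

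- **The analysis is withdrawn.** SAP 17 records the stop for futility after the first interim. Key secondary analyses will not be done and Set-2 will not be derived, so no reported result changes.
- **The test is not invalid.** A reader might infer inflated type I error. Randomisation balances follow-up, and the crude test rejects in about 1.5% of null runs against 2.5% allowed. Nor does Set-2 create an effect from nothing: with equal arms it raises both rates alike.
- **Closed-out grafts as failures.** A reader might infer that all of them count as failed, which with no drop-out and 3-year accrual would give 86% v 72%. The documents do not support this as the natural reading. SAP 10.2 assigns failure to those who discontinued, SAP 10.3 separates completing from discontinuing, and closed-out subjects have an end-of-study graft assessment. The rule is missing rather than wrong.
- **A fixed 51 after a sample size increase.** A reader might infer that closure would then come even earlier. The documents state no other target, but they do not say that 51 would be kept.
- **Survival analyses are planned.** SAP 10.3 has Kaplan-Meier and proportional hazards analyses of time to all-cause graft failure, though outside the confirmatory test.
- **The event count may fall short.** If 51 failures never occur, all remaining subjects are followed to 4 years and the problem does not arise at the final analysis.

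None of this supplies the missing rule, makes an interim crude proportion a 4-year one, or removes the outcome condition from Set-2.

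**Conclusion.** The point holds for the plan as designed. A fixed-time proportion, event-driven looks and closure, a test blind to follow-up, and no rule for working grafts short of Month 48 do not fit together. That mismatch, and the outcome-dependent entry to Set-2, can be read from the text without simulation.

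The size rests on the plan's rates and drop-out plus assumed constant hazards and accrual of 3 to 8 years. On those, early closure happens in roughly four trials in five. The observed rates are several points below the 4-year rates, Set-2 overstates failure in both arms, and Fisher gives up about 8 points of power against the log-rank test. Part of that power gap comes from counting drop-outs as failures under Fisher and censoring them under log-rank. The damage is to interpretation and power, not to error control, and the abbreviated report is unaffected.

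**What to change.** In SAP 2.6, 4.6 and 10.2 and Protocol 9.7 and 9.8.2.1:

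- Make the confirmatory key secondary test a log-rank test of time to all-cause graft failure at 26, 39 and 51 events. Keep the existing boundaries, which are already indexed by events.
- Report failure proportions at Month 48 by Kaplan-Meier. State that subjects closed out by the event-driven stop are censored at their last graft assessment, in line with SAP 10.3.
- Reconcile whether death is an event. Table 2, footnote a, includes death in the 51 graft failures; the SAP 10.2 definition does not list it and the SAP 10.3 censoring rules for graft failure do not mention it.
- Define Set-2 by doses and deviations only, without the 4-year assessment condition.

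The cost is wording; no new data are needed. The downside is small: the headline test becomes time-to-event, and the Month 48 estimate has a wider interval because it reflects the follow-up actually available. Following every subject to 4 years would also remove the mismatch at the final analysis, at the price of a longer study, but not at the interim looks.
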